## 8. RESEARCH QUESTION AND OBJECTIVES

### 8.1. Research Question

The study's research questions are related to characterizing the long-term safety and tolerability of tofersen in routine clinical practice among adults with ALS who have a mutation in the *SOD1* gene.

All objectives will be stratified by tofersen treatment status except secondary objective 2 (assessed among tofersen users only). All data will be summarized by descriptive statistics.

### 8.2. Primary Objectives

1. To describe demographic and clinical characteristics of people with *SOD1*-ALS.
2. To describe the frequency of SAEs among people with *SOD1*-ALS, including serious neurologic events previously reported in clinical trial participants (e.g., myelitis, radiculitis, aseptic meningitis, increased intracranial pressure, and/or papilloedema).

### 8.3. Secondary Objectives

1. To describe the frequency of new comorbid conditions, pregnancy and pregnancy outcome among people with *SOD1*-ALS.
2. To describe the frequency of treatment discontinuation among people with *SOD1*-ALS treated with tofersen.

- █ [REDACTED]
1. [REDACTED]
  2. [REDACTED]
  3. [REDACTED]

---

 An SAE in this registry-based study protocol is any untoward medical occurrence, that, regardless of treatment status, meets the criteria listed in Section 16.

CONFIDENTIAL

The information contained herein may not be used, disclosed, or published without the written consent of Biogen MA Inc.

## 9. RESEARCH METHODS

### 9.1. Study Design

This study is an observational, registry-based study of people with *SODI*-ALS using data collected by 2 existing networks of ALS disease registries: 1) the TRICALS network's Precision-ALS programme with data from participating clinical centres across multiple European countries and 2) ALS/MND NHC with data collected from clinical centres in the United States. The data is collected via disease registry networks of prospective observational cohort design and consolidated in shared data platforms. All data are collected by the registry networks as part of their longitudinal data collection, and for the purposes of this study, the analysis of the data is considered secondary use of the registry data. As the data in the registries are collected according to routine clinical practice and their respective observational plans, there are no interventions proposed that might pose any additional risk.

Participants are expected to be followed in the registry networks as per their respective protocols until death or loss to follow-up. The study will be based on the routine medical care in the geographies. The study will include data on all *SODI*-ALS cases enrolled in the Precision-ALS platform and ALS/MND NHC, including prevalent *SODI*-ALS cases at the start of data collection and incident *SODI*-ALS cases, irrespective of tofersen treatment status. The assessment of incident drug users is a key feature to avoid immortal time bias [Suissa 2008] and depletion of susceptibles in real-world evidence studies [Moride and Abenheim 1994]. However, in the case of ultra-rare diseases (< 1 case per 50,000 population) like *SODI*-ALS [Brown 2021], the inclusion of prevalent *SODI*-ALS cases including tofersen users at the start of data extraction will allow the collection of as much data as possible.

All endpoints will be stratified by tofersen treatment status except secondary endpoint 2 (assessed among tofersen users only). All data will be summarized by descriptive statistics.

#### 9.1.1. Primary Endpoints

1. Demographic and clinical characteristics, using descriptive statistics.
2. Frequency of SAEs.

#### 9.1.2. Secondary Endpoints

1. Number and proportion of participants with new comorbid conditions, pregnancy, and pregnancy outcome.
2. Number and proportion of participants with reported treatment discontinuation and listing of reported reasons for discontinuation.

1. [REDACTED]

CONFIDENTIAL

The information contained herein may not be used, disclosed, or published without the written consent of Biogen MA Inc.

2.

3.

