## 7. RATIONALE AND BACKGROUND

### 7.1. Introduction

Amyotrophic lateral sclerosis (ALS), also known as motor neuron disease (MND), is a rare, progressive, and ultimately fatal neurodegenerative disease that causes loss of motor neurons in the brain and the spinal cord that are responsible for controlling voluntary muscle movement. The progressive loss of motor neurons typically leads to paralysis and ultimately death from respiratory failure.

The prevalence in Europe is estimated to be approximately 6.55 per 100,000 persons based on the pooled prevalence estimates of individual studies in Europe excluding the United Kingdom (UK) [Brown 2021]. In approximately 2% of people living with ALS, the disease is attributed to mutation(s) in the gene encoding the enzyme superoxide dismutase 1 (SOD1) [Bunton-Stasyszyn 2015], hereafter referred to as *SOD1*-ALS.

Though the mechanisms by which mutations in *SOD1* cause degeneration in ALS are not fully understood, mutations in this gene are thought to cause an accumulation of toxic forms of SOD1 protein via a gain of function mechanism [Trist 2022; Trist 2021]. This neurotoxic property can arise from various primary causes, all of which increase the propensity of the SOD1 protein to aggregate [Allen 2003; Andersen 1995; Bruijn 1998; Ekhtiari Bidhendi 2018; Ilieva 2009; McCampbell 2018; Saccon 2013; Sau 2007]. Over 200 causative *SOD1* mutations associated with ALS have been identified to date [ALSoD 2023], with a median survival time of 2.3 years [Opie-Martin 2022], although heterogeneity exists between *SOD1* mutation types [Huang 2024].

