## 9.7. Data Analysis

Planned analyses are summarized below and will be described in more detail in a separate statistical analysis plan (SAP).

Data will be analyzed separately for each registry network. However, the analysis performed will be harmonized as much as possible, where data capture and actual participant and event numbers allow.

Statistical analyses will generally be descriptive in nature and there is no *a priori* hypothesis to be tested. Continuous variables will be described with summary statistics including number of observations, mean, standard deviation, median, first quartile, third quartile, and minimum and maximum values. Categorical data will be described in terms of frequencies and percentages. An additional category of 'missing' will be added to account for missing data. Event rates may also be calculated as deemed appropriate.

All efforts will be made to collect data as completely as possible but incomplete dates could occur and this must be considered when evaluating the event and censoring times. Partial dates with missing information will be imputed as detailed in the SAP.

Analyses will be conducted on all adults with *SODI*-ALS enrolled in Precision-ALS and ALS/MND NHC, including participants treated with tofersen as well as untreated participants. All analyses will be stratified by tofersen treatment status except secondary objective 2 (assessed among tofersen users only). Further details on the exclusion of data from clinical trials and the impact on index dates will be detailed in the SAP.

Comparisons between treated and untreated patients for outcomes related to safety, tolerability, or effectiveness are not planned, owing to the inability to address bias in the analyses, given the small sample size for *SODI*-ALS and uncertainties around patient selection for tofersen treatment.

All participants, including participants who discontinue tofersen, will be followed until death or loss to follow-up. Sensitivity analyses will be performed censoring data 150 days (5 half-lives) after tofersen discontinuation (after which data will then be excluded from the analysis) [Benet and Zech 1981; FDA 2003; Rowland and Tozer 2010].

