Data collected while a person with *SODI*-ALS is participating in an interventional clinical trial (with tofersen or any other investigational medicinal product) will be excluded since this study will focus on real-world data and the results from interventional clinical trials will be available elsewhere.

CONFIDENTIAL

The information contained herein may not be used, disclosed, or published without the written consent of Biogen MA Inc.

The analysis population and definition of index date for statistical analysis will differ by treatment status and by study objective. In general terms, index date will be the date of tofersen treatment for data from participants in the treated group or date of enrolment into the registry for data from participants in the untreated group [REDACTED]

[REDACTED] Sensitivity analyses will be performed excluding retrospectively treated participants (i.e., those who initiated tofersen treatment prior to enrolment in the registry networks).

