#### **9.7.2.2. Treatment Discontinuation**

Summary statistics of the duration of treatment use and prescribed dosing frequency will be provided among people with *SOD1*-ALS receiving tofersen. Frequency and proportion of participants with treatment discontinuation will be reported. Reported reason for treatment discontinuation will be tabulated.

CONFIDENTIAL

The information contained herein may not be used, disclosed, or published without the written consent of Biogen MA Inc.

[REDACTED]

[REDACTED]

[REDACTED]

[REDACTED]

[REDACTED]

[REDACTED]

[REDACTED]

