**Tofersen treatment log**

Variables	Data type / categories and responses
Treatment start date	[date]
Infusion dates	[date]
Dose	[numeric]
Dose unit	[Text field, values predefined]
Dose change	Y/N
Reason for dose change	[Text field]
Treatment discontinuation	Y/N
Treatment discontinuation date	[date]
Reason for discontinuation	Death 
	SAE 
	Healthcare provider decision
	Patient preference
	Other Specify [text field]
	Unknown

Details captured on mortality form

Prompt to SAE form

CONFIDENTIAL

The information contained herein may not be used, disclosed, or published without the written consent of Biogen MA Inc.

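### The discontinuation endpoint is a crude all-reason proportion with death as a coded reason, so it rises with mortality and follow-up whatever the tolerability

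*Protocol*

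**What the plan says.** Section 9.1.2 states the endpoint as "Number and proportion of participants with reported treatment discontinuation and listing of reported reasons for discontinuation". Section 9.7.2.2 repeats the measure: "Frequency and proportion of participants with treatment discontinuation will be reported". It adds two companions: "Reported reason for treatment discontinuation will be tabulated", and "Summary statistics of the duration of treatment use and prescribed dosing frequency will be provided". Neither section fixes a time point, a person-time denominator or the handling of death.

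In Annex 4, the tofersen treatment log lists death first among the reasons for discontinuation, with the footnote "Details captured on mortality form". The other reasons are SAE, healthcare provider decision, patient preference, other (with free text) and unknown.

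Section 9.2.3 admits participants over the first 5 years of a 7-year study, which allows 2 years of follow-up for Year 5 entrants. It also provides for all available data to be reported at each annual reassessment. Section 7.1 describes *SOD1*-ALS "with a median survival time of 2.3 years". Section 9.7 says that, in general terms, the "index date will be the date of tofersen treatment for data from participants in the treated group", and that index dates will differ by objective. It also allows rates: "Event rates may also be calculated as deemed appropriate".

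**The concern.** A proportion of everyone ever treated has a clear meaning only if all participants are observed for a similar time, or if the event is read off at a fixed time. Here observation times differ by years and the disease is fatal. Participants still on treatment move into the numerator when they die, because the log codes death as a discontinuation reason and nothing in 9.1.2 or 9.7.2.2 removes it.

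The research question in section 8.1 includes tolerability. A reader of successive annual reports would see the proportion climb and could take this for growing intolerance, when it may reflect only deaths and a longer-observed cohort. The same problem affects any comparison between the two registry networks, which are analysed separately, if their follow-up differs.

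**Working it through.** The protocol gives no projected figure for this endpoint. Its study size does reproduce: 25 × 5 = 125 cases; 125 × 0.40 = 50 treated; 50 × 2 years = 100 person-years.

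**Inputs**
- Median survival 2.3 years (section 7.1). No time origin is stated and it is not given as survival from tofersen start. Alternatives, both assumed: 2.0 years (borrowed from the follow-up assumption in section 9.5) and 4.6 years (double).
- Entry over 5 years, end at 7 years (section 9.2.3), so potential follow-up C is uniform on 2 to 7 years at the end.
- Rate of stopping for reasons other than death, s: not in the protocol; assumed 0.10 to 0.30 per year.
- Constant hazards, no loss to follow-up, treatment starting at entry: assumed.

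**1. Deaths alone (s = 0).** Death hazard m = ln 2 / median; proportion by time T = 1 − exp(−mT).

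| Median | m per year | 1 y | 2 y | 5 y | 7 y |
|---|---|---|---|---|---|
| 2.3 y | 0.301 | 26% | 45% | 78% | 88% |
| 4.6 y | 0.151 | 14% | 26% | 53% | 65% |

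These are the values the endpoint would take if nobody stopped for any reason but death.

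**2. Share of discontinuations that are deaths**, m / (m + s):
- Median 2.0 y (m = 0.347), s = 0.10: 0.347 / 0.447 = 78%.
- Median 2.3 y, s = 0.30: 0.301 / 0.601 = 50%.
- Median 4.6 y, s = 0.10: 0.151 / 0.251 = 60%; s = 0.30: 0.151 / 0.451 = 33%.

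So the range is 50–78% with a 2–2.3-year median and 33–60% with 4.6 years. The share falls to one half when s = m, that is at 0.30 per year (2.3 y) or 0.15 per year (4.6 y).

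**3. Drift between reports.** Take the 2.3-year median and s = 0.10, so h = m + s = 0.401. For follow-up uniform on (a, b), the expected proportion is 1 − [exp(−ha) − exp(−hb)] / [h(b − a)].
- Report at year 1, C on (0, 1): 18%.
- Report at year 5, C on (0, 5): 57%.
- End, C on (2, 7): 81%.

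Taking deaths out but keeping n/N multiplies each by s/h = 0.249, giving 4%, 14% and 20%. The stopping rate is constant throughout. Removing deaths lowers the level but leaves the drift with follow-up.

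**4. Fixed-time cumulative incidence.** With s = 0.10, non-death discontinuation by T is (s/h)[1 − exp(−hT)].
- 12 months: 8.2% (2.3 y) and 8.8% (4.6 y).
- 24 months: 13.8% (2.3 y) and 15.7% (4.6 y).

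The all-reason proportion at 24 months is 55% and 39% in the same two cases. The fixed-time measure does not depend on when the report is cut and is much less sensitive to the survival assumption.

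**5. Precision.** 50 × 0.138 ≈ 7 events by 24 months. Ignoring censoring, 7/50 has an exact binomial 95% interval of about 6% to 27%.

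**The case against.** The strongest reply is that the stated objective is only to describe the frequency of discontinuation, which an all-cause count does. Reasons are tabulated, death and SAE are separate codes, and duration of treatment use is summarised. Rates are permitted by section 9.7, and time-to-event detail may be in the SAP.

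Much of this stands. A reader might infer that the endpoint cannot separate intolerance from death. It can, as a count: the table less its death row. A reader might also infer that the proportion will mostly measure mortality. The protocol does not establish that. The 2.3 years is a general figure that varies by mutation type. The median trial exposure in section 7.2, 148.4 weeks (148.4 / 52.18 = 2.84 years), is already longer, so mortality on treatment may be lower than assumed here. Nor is this the only information on tolerability, since SAE relationship, action taken and dose changes are also collected.

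An immortal-time error for participants who started before enrolment is another tempting reading. The index date is given only in general terms, its detail is left to the SAP, and a sensitivity analysis excluding these participants is planned. The error cannot be asserted from this document.

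What the reply does not meet is unequal follow-up. The table of reasons has the same denominator problem. The rate clause is optional and general; it is repeated for SAEs (9.7.1.2) and comorbid conditions (9.7.2.1) but not for discontinuation (9.7.2.2).

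**Conclusion.** The point holds as a matter of how the endpoint is built. As written, secondary endpoint 2 is a crude all-reason proportion that can include deaths on treatment, over potential follow-up of about 2 to 7 years. It rises with mortality and time whatever the tolerability and is not comparable between annual reports. Deaths alone would carry it from 26% at 1 year to 88% at 7 years at the protocol's median survival, or from 14% to 65% at twice that median.

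The size is illustrative: it rests on exponential survival, and steps 2 to 4 of the working also rest on an assumed non-death stopping rate. That deaths would form the majority is conditional on that rate being below about 0.30 per year (2.3-year median) or 0.15 per year (4.6-year median). The endpoint is descriptive and secondary, so no test or comparison is at risk. The change is worth making because the figure will be reported repeatedly and is easily misread.

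**What to change.** In sections 9.1.2 and 9.7.2.2:
- Define discontinuation as stopping tofersen for a reason other than death, and show deaths on treatment on a separate line.
- Report the cumulative incidence of non-death discontinuation at 12 and 24 months from initiation (Aalen-Johansen), with death as the competing event.
- Let participants who started before enrolment enter the risk set at enrolment (delayed entry).
- Keep n/N and the table of reasons as companions.

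Optionally, ask the registries for a reason code for non-serious adverse events; otherwise classify these from the free text under the other category.

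The cost is mainly wording. The treatment log already holds the start date, discontinuation date and reason, and deaths go to a mortality form. The drawback is small numbers: about 50 treated participants in all, with the networks analysed separately, so intervals will be wide and early risk sets may be thin under delayed entry. Curves by reason should be limited to where counts allow. The optional code means one extra category for both registries.

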## 9.2. Setting

### 9.2.1. Selection Criteria

Adults with *SOD1*-ALS enrolled in TRICALS network's Precision-ALS programme with data from participating clinical centres across multiple European countries or at ALS/MND NHC with data from participating clinical centres in the United States (tofersen users and tofersen non-users). The 2 networks of ALS registry platforms/consortia are considered representative of people diagnosed with *SOD1*-ALS in Europe and the United States.

### 9.2.2. Study Location

This study will leverage data on people with *SOD1*-ALS collected by the TRICALS network's Precision-ALS programme in multiple European countries including Ireland, Portugal, Netherlands, Belgium, Sweden, Switzerland, UK, Italy, Spain, Germany, France and ALS/MND NHC in the United States. In the case that the registry networks expand, any new countries and sites contributing data to the Precision-ALS platform may be considered for inclusion in this study. New countries and sites contributing data to ALS/MND NHC may be considered for inclusion in this study, if the contributing countries do not overlap with participating countries already included in this study as part of the Precision-ALS programme to avoid duplicate reporting on the same person with *SOD1*-ALS.

### 9.2.3. Overall Study Duration and Follow-Up

All participants with an ALS diagnosis and a confirmed *SOD1* mutation from contributing registry networks will be considered for inclusion in the study. Although this specific obligation currently has an unlimited duration, for the purpose of planning (e.g., final report), the study protocol plans for the end of data extraction for this study to be 7 years after the study start. Participants present or entering the registries during the first 5 years of the study may be included in the analyses, and the 7-year study duration allows the possibility for 2 years of follow-up for patients entering in Year 5. The expected end date may be modified based on study progress, which will be reviewed annually as part of the reassessment procedure.

Follow-up data are collected by the registry networks as part of their longitudinal data collection. All data are collected according to routine clinical practice in routine encounter-based clinic visits per the registry networks' protocols, which may occur at differing intervals, depending on the local standards for patient care. Participants are expected to be followed in the registry networks as per their respective observational

CONFIDENTIAL

The information contained herein may not be used, disclosed, or published without the written consent of Biogen MA Inc.

plans until death or loss to follow-up, regardless of tofersen treatment status. The contributing registries will not include data from participants who have withdrawn the required consents. For this study, all available data will be obtained and reported as part of the annual reassessment procedure throughout the study period.

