## 6. MILESTONES

**Table 2: Milestones for Protocol 233AS401**

Milestone	Planned Date
Start of data collection (data extraction) a	30 January 2026
End of data collection (data extraction) a, b	30 July 2033
Interim progress reports	Annually (with reassessment)
Registration in HMA-EMA catalogue of real-world data studies c	31 October 2025
Report of study results	Within 12 months of end of data collection (data extraction)

a Per European Union (EU) Guideline on good pharmacovigilance practices ([[EMA \(EMA/330405/2012\) 2012](#)] Section A.1), the start and end of data collection for secondary use of data are the date from which data extraction starts and the date from which the analytical datasets are available.

b The end of data extraction for this study is set to 7 years from start of data extraction. The expected end date of data extraction may be modified based on study progress, which will be reviewed annually as part of the reassessment procedure. The potential continuation of the study will be determined based on the results obtained at the targeted end of data collection (data extraction).

c Study will be registered in Heads of Medicine Agency-European Medicines Agency (HMA-EMA) catalogue of real-world data studies following Pharmacovigilance Risk Assessment Committee approval of final protocol and prior to study initiation.

CONFIDENTIAL

The information contained herein may not be used, disclosed, or published without the written consent of Biogen MA Inc.

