#### 9.5. Study Size

Data will be extracted on all *SODI*-ALS cases enrolled or entering in the Precision-ALS platform and ALS/MND NHC registry networks at study start and data on all incident *SODI*-ALS cases enrolling in the registry during the first 5 years of the study. Thus, participants present or entering the registry networks during the first 5 years of the study may be included in the analyses. Given the difficulty in predicting enrolment of

CONFIDENTIAL

The information contained herein may not be used, disclosed, or published without the written consent of Biogen MA Inc.

*SODI*-ALS cases, the study will monitor enrolment and reassess the enrolment period duration while the study is ongoing.

For a 5-year enrolment period, assuming a total of 25 *SODI*-ALS cases per year could be enrolled, approximately 125 cases could be expected across both registry networks. Participants are expected to be followed in the registry networks as part of their respective observational plans until death or loss to follow-up, regardless of tofersen treatment status. Assuming a median follow-up time of approximately 2 years [Opie-Martin 2022], an enrolment of 25 cases per year, and an estimate of 40% tofersen treatment proportion, 100 person-years of follow-up data could be expected among tofersen-treated participants which will allow evaluation of the incidence of serious neurological events. Therefore, the target study size is at least 100 person-years of follow-up from tofersen-treated participants or at least 125 total *SODI*-ALS cases (tofersen-treated or untreated) during the first 5 years of the study. The enrolment period is currently planned for a minimum of 5 years, and the suitability of that time frame will be reassessed during the study.

Limited data are available on the expected incidence of serious neurologic events. Using findings from the 147 tofersen treated (100 mg) participants in the Study 233AS101 (EudraCT number: 2015-004098-33) and Study 233AS102 (EudraCT Number: 2016.003225-41) integrated population over approximately 2.5 years exposure, a total of 12 serious neurologic events in 10 participants were reported for a combined rate of 0.033 events per person-year.

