This study will include data from both prevalent and incident tofersen users. The assessment of incident drug users is a key study design feature to avoid immortal time bias [Suissa 2008] and depletion of susceptibles in real-world evidence studies [Moride and Abenheim 1994]. However, in the case of ultra rare diseases like *SODI*-ALS, the inclusion of participants with prevalent *SODI*-ALS, including tofersen users at the start of data extraction, will allow the collection of as much data as possible. The potential biases resulting from inclusion of prevalent users is acknowledged, and the analysis will take these potential biases into consideration (e.g., reporting results separately for prevalent and incident tofersen users if deemed appropriate). The safety profile of tofersen will be characterized through a review of the SAE data reported from individual participants during the study with a particular focus on the relationship assessment recorded on the SAE forms, temporal relationship of SAEs to tofersen dosing, the

CONFIDENTIAL

The information contained herein may not be used, disclosed, or published without the written consent of Biogen MA Inc.

consistency of SAE reports with tofersen clinical trial data and published literature, biologic plausibility, and confounding factors including known comorbidities of ALS.

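### The plan extracts data to Year 7 but gives people who enter the registries after Year 5 no place in the analysis, although a rate per person-year could use their data

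*Protocol*

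**What the plan says.** Section 9.2.3 sets the analysed cohort: "Participants present or entering the registries during the first 5 years of the study may be included in the analyses". Section 9.5 and the abstract use nearly the same sentence and refer to incident cases enrolling in the first 5 years. Section 9.2.3 gives one reason: "the 7-year study duration allows the possibility for 2 years of follow-up for patients entering in Year 5". The footnote to Table 2 fixes the other end: "The end of data extraction for this study is set to 7 years from start of data extraction".

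The 5-year period is not final. Section 9.5 adds: "The enrolment period is currently planned for a minimum of 5 years, and the suitability of that time frame will be reassessed during the study". The end date is also reviewed each year.

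Three other statements bear on the point. Section 9.2.3 says that everyone with ALS and a confirmed mutation will be considered for inclusion, and that all available data will be reported over the study period. Section 9.9, on sample size, aims to maximise the number of people and applies no exclusion criteria. Sections 9.1 and 9.9 accept prevalent users, despite the known biases, in order to collect as much data as possible.

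**The concern.** The registries go on enrolling, and the sponsor goes on extracting, for two years after the entry window closes. The study is sized on serious neurologic events per person-year with a Poisson interval (Section 9.5, Table 3). In that summary each person contributes the time observed, and someone with six months of follow-up contributes half a person-year. The plan requires no minimum follow-up of anyone else, since follow-up ends at death or loss whenever that occurs. Allowing 2 years for a Year 5 entrant is therefore a reason to extract until Year 7, but not a reason to leave a Year 6 entrant out of the rate.

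What is at stake is some person-time and, possibly, individual events. At the target size the plan expects about 4 serious neurologic events. If the 5-year minimum is not extended, an event in a treated person who entered the registry in Year 6 or 7 has no stated place in the analysis.

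**Working it through.** **Inputs.** Section 9.5 gives "an enrolment of 25 cases per year, and an estimate of 40% tofersen treatment proportion", a 5-year enrolment period, a median follow-up of about 2 years and a rate of 0.033 events per person-year. Section 7.2 gives 368.83 participant-years of trial exposure.

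**The plan's own figures reproduce.**
- Cases: 25 × 5 = 125.
- Treated person-years: 125 × 0.40 × 2 = 100.
- Rate: 12 / 368.83 = 0.0325, stated as 0.033.
- Table 3 at 100 person-years: 0.033 × 100 = 3.3, rounded up to 4. The exact Poisson 95% limits are χ²(0.025; 2k)/(2T) and χ²(0.975; 2k+2)/(2T). With k = 4 and T = 100 they are 0.0109 and 0.1024, half-width 0.0458, as printed. The other four rows also reproduce.

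**Treated entrants in Years 6-7.** 25 × 2 × 0.40 = 20.

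**Their person-years to the end of Year 7.** Entry is taken as uniform, with the plan's rates continuing. A late entrant's possible follow-up is then uniform on 0 to 2 years.
- Exponential follow-up with a 2-year median, λ = ln 2 / 2 = 0.3466: mean = [1 − (1 − e^(−2λ))/(2λ)]/λ = 0.804 years, so 20 × 0.804 = 16.1.
- No deaths or losses before the end of Year 7: 20 × 1 = 20, an upper limit.

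**Base from Year 1-5 entrants.** 50 treated, possible follow-up uniform on 2 to 7 years, same λ: mean = [1 − (e^(−2λ) − e^(−7λ))/(5λ)]/λ = 2.200 years, so 50 × 2.200 = 110.0. Prevalent cases at study start are not counted.

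**Relative gain.** 16.1/110 = 14.6% and 20/110 = 18.2%. With a flat 2 years each, as in the plan's own product, it is 20/100 = 20%. With an exponential of mean 2 years it is 14.7/86.5 = 17%.

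**Expected extra serious neurologic events.** 0.033 × 16.1 = 0.53 and 0.033 × 20 = 0.66.

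**Precision, with expected events left unrounded (k = 0.033T).**

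| Person-years | Expected events | Half-width | Change |
|---|---|---|---|
| 100 → 116 | 3.30 → 3.83 | 0.0423 → 0.0387 | −8% |
| 110 → 126 | 3.63 → 4.16 | 0.0400 → 0.0369 | −8% |

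Table 3's rule of rounding up makes such comparisons erratic. From 100 to 116 the count stays at 4 and the half-width falls from 0.0458 to 0.0394 (−14%). From 110 to 126 the count steps from 4 to 5 and it falls from 0.0416 to 0.0399 (−4%). The unrounded figure is the fairer one.

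**Length of extraction.** The dates in Table 2 (30 January 2026 to 30 July 2033) are 7.5 years apart, not 7. With extraction to 7.5 years and entry open throughout, the 2-year-median model gives 23.9 added person-years on 115.5, and 0.79 expected event.

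**The case against.** The strongest reply is that nothing is fixed or thrown away. Five years is a minimum, the enrolment period is to be reassessed, and the inclusion sentence is permissive. This stands: a reader might infer that data on later entrants will be discarded, and the protocol does not say so. It also does not say that they will be used. The reassessment concerns how long enrolment lasts, and no rule is given for person-time after it closes.

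Second, closing entry before the data cut is ordinary practice. The secondary endpoints are numbers and proportions of participants, and event rates are only to be calculated where appropriate. Short follow-up does dilute crude proportions, so this is a fair reason to show proportions both ways. It does not reach the person-year rate on which the study is sized.

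Third, a reader might see a contradiction with the absence of exclusion criteria in Section 9.9. That statement can be read as concerning who qualifies, while an accrual window concerns when people enter. The two are in tension, but do not contradict each other.

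Fourth, a reader might take later entrants to be mostly new users observed with SAE forms from the first dose, and so the cleanest data. The protocol gives no such share, and Section 9.7 expects some people to start tofersen before registry enrolment. Conversely, registry members enrolled by Year 5 who start tofersen in Years 6-7 are not affected by the limit.

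Finally, the target is reached without these people on the plan's inputs: 100 person-years by its own product, 110 in the 2-year-median model. This stands and limits the weight of the point.

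**Conclusion.** The point holds as a modest design improvement and a gap in wording. The current plan analyses people present or entering in Years 1-5, extracts to Year 7, and gives later entrants no stated place. Its reason does not justify omitting their person-time and SAEs from rates, and the omission fits poorly with the aims of maximising sample size and reporting all available data.

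The cost of leaving it is about 16 to 20 treated person-years (about 15-18% on 110), about 0.5 to 0.7 expected serious neurologic event, and at 16 person-years an interval about 8% wider than it could be with them as the reference's gain. No stated objective fails. The figures assume 25 cases a year and 40% treated continuing through Years 6-7, uniform entry, the follow-up models shown and a 7-year extraction. Counting prevalent cases at study start would enlarge the base and reduce the relative gain.

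**What to change.** In Sections 9.2.3 and 9.5 and in the abstract, state that everyone entering the registries up to the last data extraction contributes person-time and SAEs to the SAE counts and rates. Show crude participant proportions with and without people who enter after Year 5. The 5-year period can remain as the planning basis for the study-size target.

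The cost is wording in three places and the removal of a date restriction in the analysis. The records come from registries already being extracted, so nobody has to be recruited for it. The small downside is that later entrants have under 2 years of follow-up in a 7-year extraction, which dilutes crude proportions; the two-way display deals with that.
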